# RESEARCH PLAN

## 1.1 Summary

We propose to test our central hypothesis that readmission and post-discharge utilization in high risk medical and surgical patients can be reduced by using a vendor platform (PinpointIQ from the company physIQ) that involves wearable sensors (Vital Patch) that collect real-time, continuous ambulatory vital signs, a mobile device that collects patient reported outcomes and machine learning algorithms in the cloud that identify patients at risk of physiologic perturbation. Data from this vendor platform will be tied to operational workflows at NorthShore that involve a monitoring nurse who then conveys information to the clinical team as necessary in a cascading alert system.

## 1.2 Background and Significance

Hospital readmissions are common and costly and are increasingly being used as a metric for quality care. With the passing of the Affordable Care Act (ACA) hospital readmissions were targeted with the Hospital Readmission Reduction Program (HRRP) in which hospitals are penalized for higher than expected readmission rates. Significant effort has been devoted to understanding how to reduce readmissions and utilization. To date there has been limited work looking at how wearable sensors that monitor physiologic data continuously and remotely can identify physiologic perturbation allowing care providers ample time to intervene and prevent decompensation and readmission.

Monitoring of vital signs for hospitalized patients to detect decompensation is checked manually and intermittently (spot check) for the majority of patients. When patients are discharged, vital signs are frequently not monitored in the 30-day readmission window. This lack of monitoring in the post discharge period may prevent identification of patients at risk of decompensation and readmission. When spot vitals are monitored at home, reductions in readmission rates for certain populations have been seen.

New technology in wearables coupled with machine learning algorithms is able to detect vital signs remotely and continuously and correlate the output with signals that may indicate risk of physiologic perturbation. Various studies have looked at how continuous monitoring of vitals can identify patients in the hospital quicker and more effectively than nurse driven spot checks of vital signs. There is a lack of data on using these devices upon discharge to evaluate for decompensation and prospectively trying to reduce readmissions. Similarly, there is a lack of data in tying these devices to a cascading and escalating alert system to identify patients at risk of decompensation. There is qualitative data on looking at how wearables are perceived by providers and patients in the hospital but there is a lack of data on perception of this technology for remote monitoring.

Postoperative ileostomy patients are frequently readmitted because of physiologic perturbation and has readmission rates between 15-30% at NorthShore. Ileostomy patients are readmitted because of dehydration. There has been early work establishing the predictive potential of multivariate physiological telemetry (pinpointIQ) from a wearable sensor providing accurate early detection of impending rehospitalization for postoperative ileostomy with a predictive accuracy comparable to implanted devices. This population may benefit from remote continuous monitoring of vital signs tied to a cascading alert system to identify patients at risk of impending decompensation. There is limited literature looking at how continuous monitoring, ambulatory wearable devices can improve outcomes in high risk patients.

We propose conducting a mixed-methods study that will use a wearable device to collect ambulatory physiological data analyzed by a machine-learning algorithm to identify readmission risk. The alerts will be tied to a cascading escalation pathway that involves monitoring nurse, mid-level providers, specialists, and surgeons. We describe the quantitative and qualitative aspects of the study in detail below.

# QUANTITATIVE

## 2.1 Quantitative Research Aims – Ileostomy Cohort

Aim 1: Determine if wearable technology deployed for 30 days in a high-risk patient population can augment 30-day readmission risk prediction and improve care processes via an escalating feedback protocol.

Aim 2: Understand and finalize thresholds and criteria for alert system at the levels of Vital Patch, physIQ's pinpointIQ, monitoring RNs for ileostomy patients

Aim 3: Finalize process maps and workflows for nurse navigators and clinical care teams that optimize identifying high risk patients while minimizing provider burden

Aim 4: Calculate the return on investment of the remote monitoring solution

Aim 5: Perform a deep analysis of the full process to understand effectiveness, feasibility, efficiency and bottlenecks

## 2.2 Experimental Plan and Methods

The goal of the study is to reduce readmission rates for high risk medical and surgical patients. The goal of the study is to understand how physIQ's platform Pinpoint IQ with a cascading set of alerts including the wearable device alerts, patient reported metrics, CAPE navigator or monitoring nurse alerts can be developed and improved upon to reduce the incidence of 30 day readmission. We will be enrolling 10 colorectal (post ileostomy formation) patients who will be using a standardized set of cascading alerts that have been fine tuned with the goal of reducing decompensation and 30-day readmissions.

### ***Ileostomy***

For the colorectal patients, we will attempt to enroll every patient that has a colectomy followed by ileostomy formation. These will be patients of Drs. [name], [name], and [name] and will be at Evanston, Glenbrook, and Highland Park hospitals. The colorectal surgeons will notify the study team when a patient has undergone surgery and the research coordinator will perform recruitment. Patients will be approached by the study coordinator who will perform informed consent. If the patient is agreeable the patient will receive a kit from physIQ prior to discharge. A Vital patch will be placed on the patient prior to discharge and the patch will be connected via blue tooth to the physIQ mobile device and pinpointIQ application. The study coordinator will teach the patient how to apply and remove the patch and what to do if there are issues with the patch. The study coordinator will also teach the patient how to use the mobile device and the physIQ application. This will also occur immediately prior to discharge.

On discharge colorectal patients will be asked questions every morning and every afternoon from the pinpoint IQ application. The pinpoint IQ platform will query patients about their ostomy output every

morning. We would also ask if the patient has any infectious symptoms such as fever, discharge or redness around the incision site or stoma and if the patient has any dehydration symptoms such as decreased urine output, dark urine, or obstruction and other alarming symptoms that the team would like to know about. In the afternoon, the symptom questions will be asked again. The monitoring nurse will evaluate the pinpoint IQ in the morning after the patient has filled out the questionnaire and in the afternoon after the patient has filled out the symptom question again. They will evaluate the responses to the questions and the physiologic alerting system built by physIQ. There will again be an algorithm built within physIQ's system that provides an alert to the monitoring nurse if the criteria from Table 4 are met.

*(Output volume - Morning question once a day)*

**Question 1:** What is your ostomy output volume in the last 24 hours?

*(Yellow and Red Zone symptom questions twice a day – 8am and 3pm)*

**Question 2:** Do you have the following symptoms?

- Eating and drinking make you nauseous or vomit
- You notice dark urine or less urine
- You can't eat or drink anything for 12 hours
- You have a fever over 101.5F

**Question 3:** Please select if you are experiencing following symptoms:

Your surgical wound is:

- Red
- Leaking liquid, blood, or pus
- Opening up or getting worse

**Question 4:** Please select if you are experiencing following symptoms:

Your belly is:

- Swelling up and feels very firm
- Hurting and the pain medication don't help

**Question 5:** Please select if you are experiencing following symptoms:

Your ostomy is:

- Leaking, or your appliances do not stay on, or you are changing your pouch more than twice a day
- Putting out more stool than usual
- Not putting out stool or gas (bag filled with air) for 6 hours

**Question 6:** If you choose any of the above symptom(s), are the symptoms getting better, worse, or the same?

- Better
- Worse
- Same
- Non Applicable

**Question 7:** If you experience the following symptoms, please call your nurse or doctor immediately, or go to the emergency room right away:

- You have trouble breathing
- You are having chest pains
- You have no urine output in 12 hours
- You are passing out

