## physIQ Alert System – Ileostomy

Patients:

Any positive symptom (dehydration, infection, or obstruction)
≥1200 ml ostomy output over one day
A high risk alert
A predefined number of standard alerts in a day

Table 4: PhysIQ alerts system for CAPE navigator or monitoring nurse for Ileostomy

For ileostomy the thresholds for the high-risk alerts and the number of standard alerts may be changed from patient to patient based on how each case progresses and the density and frequency of alerts. Determining the optimal thresholds for these two types of alerts will be a key aim of this study. The goal is again maximizing signal while minimizing noise.

If any of these conditions listed in Table 4 are met the monitoring nurse will call the patient and go through a predefined note with the following data elements and questions.

Infection Symptom
 
 
a) Fever
 
b) Dysuria
 
c) Redness at ostomy site
 
d) Drainage or swelling at ostomy site
 
e) Other (Free Text)
 

Obstruction Symptom
 
 
a) Nausea
 
b) Vomiting
 
c) Bloating
 
d) Decreased or no ostomy output
 
e) No gas through ostomy
 

Dehydration Symptom
 
 
a) Lightheadedness
 
b) Dry mouth
 
c) Low or dark urine output
 
d) Dizziness
 
e) Increased ostomy output
 

Symptom Change (Obstruction, Dehydration, Infection) [This can show up if any symptom is picked]
 
 
1. New
 
2. Worsening
 
3. Stable
 
4. Improving
 
5. Resolved
 

Ostomy output
 
 
a) 500-1200cc
 
b) >1200cc
 
c) <500cc
 

Is patient NPO? Yes/No

Is patient on antibiotics? Yes/No

Patient is on stool thickening regimen?
 
 
a) None
 
b) Metamucil powder 1 tsp bid
 
c) Imodium 2mg bid w/ meals (20 mins before meals)
 
d) Imodium 2mg qid w/ meals (20 mins before meals)
 
e) Imodium 4mg qid w/ meals (20 mins before meals)
 
f) Stool thickening managed by clinical team
 

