#### **LOGIC:**

- a) MCI, Afib w/ RVR, Tachycardia, Tachypnea (1, 3, 6)
- b) Other physiologic alert (5)
- c) Ostomy output >1200cc and patient on no stool thickening regimen (1, 5, 7, 13)
- d) Ostomy output >1200cc and patient on metamucil stool thickening regimen (1, 5, 13, 8)
- e) Ostomy output >1200cc and patient on imodium 2mg bid stool thickening regimen (1, 5, 13, 9)
- f) Ostomy output >1200cc and patient on imodium 2mg qid stool thickening regimen (1, 5, 13, 10)
- g) Ostomy output >1200cc and patient on imodium 4mg qid stool thickening regimen (1, 3, 13, 11)
- h) Ostomy output <500cc (1, 3)
- i) Has ANY Obstruction symptom, NEW, or WORSENING Obstructive Symptom, Patient not NPO (1, 3, 14)
- j) Has ANY Obstruction symptom, RESOLVED Obstructive Symptom, Patient not NPO (1)
- k) Has ANY Obstruction symptom, NEW or WORSENING Obstructive Symptoms, Patient NPO (1, 3, 14, 17)
- l) Has ANY Obstruction symptom, STABLE or IMPROVING Obstructive Symptoms, Patient NPO (17)
- m) Has ANY Obstruction symptom, RESOLVED Obstructive Symptoms, Patient NPO and Ostomy output 500-1200 (1, 3, 16)
- n) Has ANY Obstruction symptom, RESOLVED Obstructive Symptoms, Patient NPO and Ostomy output >1200, patient not on stool thickening regimen (1, 3, 16)

- o) Has the following Infectious symptoms (Redness at ostomy site, Drainage or swelling at ostomy site), NEW OR WORSENING Infectious Symptoms, Patient not on antibiotics (2, 4, 15)
- p) Has the following Infectious symptoms (Redness at ostomy site, Drainage or swelling at ostomy site), RESOLVED Infectious Symptoms, Patient not on antibiotics (2)
- q) Has the following Infectious symptoms (Redness at ostomy site, Drainage or swelling at ostomy site), NEW OR WORSENING Infectious Symptoms, Patient on antibiotics (2, 4, 15, 18)
- r) Has the following Infectious symptoms (Redness at ostomy site, Drainage or swelling at ostomy site), RESOLVED Infectious Symptoms, Patient on antibiotics (2)
- s) Has the following Infectious symptoms (Fever, Dysuria or Other), NEW, WORSENING, IMPROVING, OR STABLE Infectious Symptoms, Patient not on antibiotics (1, 3, 15)
- t) Has the following Infectious symptoms (Fever, Dysuria or Other), RESOLVED Infectious Symptoms, Patient not on antibiotics (1)
- u) Has the following Infectious symptoms (Fever, Dysuria or Other), NEW OR WORSENING Infectious Symptoms, Patient on antibiotics (1, 3, 15, 18)

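### Table 4 has no low-output alert, although output below 500 cc must be escalated; the stopped-output option in Question 5 also needs clearer wording

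*Protocol*

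**What the plan says.** All of this is in Protocol section 2.2, in the Ileostomy text, the physIQ Alert System text and Table 5.

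- **Patient questions.** Volume over the past 24 hours is asked once a day ("Output volume - Morning question once a day"). Symptom questions are asked at 8am and 3pm. Question 5 has one option for high output, "Putting out more stool than usual", and one for stopped output, "Not putting out stool or gas (bag filled with air) for 6 hours".
- **Nurse review.** The monitoring nurse opens the platform morning and afternoon, after the patient has answered: "They will evaluate the responses to the questions and the physiologic alerting system built by physIQ".
- **Automatic alert.** The vendor's algorithm alerts the nurse when a Table 4 criterion is met. Table 4 has four: any positive symptom, "≥1200 ml ostomy output over one day", a high-risk alert, and a set number of standard alerts in a day. A met criterion also leads the nurse to call the patient and work through the predefined note.
- **Predefined note.** It records output in three bands, one of them below 500 cc. Its obstruction symptoms include "Decreased or no ostomy output" and, separately, "No gas through ostomy".
- **Escalation.** Item h of the Table 5 logic reads "Ostomy output <500cc (1, 3". Actions 1 and 3 are case communication to the clinical RN and a call to the clinical RN. The text after Table 5 repeats both for output below 500 cc.

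**The concern.** The protocol treats low output as serious enough for a mandatory call to the clinical RN, but gives it no trigger in the table that generates alerts. High output has both a trigger and an action; low output has only the action.

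Low output is also a state that the protocol's own treatment could produce. The nurse may step up stool thickening daily while output is at or above 1200 ml, to as much as Imodium 4 mg four times a day, and stepping down is left to the clinical team.

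The symptom screen is the other automatic route for a patient whose output has stopped, and its one relevant option is hard to read. It joins stool and gas with an *or*, and adds a bracket about an air-filled bag, which suggests that gas is passing. A patient with gas but no stool for 6 hours may reasonably leave it blank.

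What is at stake is a delayed call for a patient with an early sign of obstruction.

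**Working it through.** The plan gives no figure to reproduce. The main check sets the texts side by side.

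**1. Volume: trigger against required action**

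| Reported 24-hour volume | Table 4 trigger | Action in Table 5 |
|---|---|---|
| High (1200 ml or more in Table 4; above 1200 cc in Table 5) | Yes | Items c to g: case communication, a call or consideration of one, IV fluids considered, thickening stepped up |
| Middle band, 500-1200 cc | None below 1200 ml | None for volume alone |
| Below 500 cc | **None** | **Item h: case communication and a call to the clinical RN** |

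The third row is the gap. Take a report of 300 ml (illustrative) with no symptom ticked and no physiologic alert. Against the four Table 4 criteria: no positive symptom, not 1200 ml or more, no high-risk alert, no count of standard alerts reached. No alert is raised. Table 5 is to be built into the electronic note that highlights recommended actions, and the stated starting point for the call and note is a Table 4 condition. So the built-in logic for item h is reached only if the nurse sees the Question 1 value and acts on it. The platform already holds that value.

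**2. Question 5: what the stopped-output option covers**

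- Read as neither stool nor gas, a patient with gas and no stool does not tick.
- Read with the bracket describing the bag, that patient does tick, but the option then contradicts its own statement about gas.
- Read as either one absent, that patient ticks.

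The documents do not say which reading is meant, and no weight is placed on any of them. A tick counts as a positive symptom under Table 4, so the reading decides whether an alert is raised.

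**3. Why the volume line does not replace the rewording**

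Assume constant output, with the stop lying within the 24 hours reported (neither is in the documents). A 6-hour stop leaves (24 − 6)/24 = 0.75 of the usual daily volume V.

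- V = 667 ml: 0.75 × 667 ≈ 500 ml
- V = 800 ml: 600 ml
- V = 1000 ml: 750 ml
- V = 1199 ml: 899 ml

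At about 667 ml a day or more, a 6-hour stop alone would not bring the reported volume below 500 ml. The two changes therefore cover different situations.

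**4. Ceiling on use**

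- Daily volume reports: 10 patients × 30 days = 300.
- Symptom sessions: 10 × 30 × 2 = 600.

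**The case against.** The strongest reply is that the low-output pathway does not need an alert. The nurse reads the answers twice a day whether or not one fires, the volume is among those answers, and item h tells the same nurse what to do. Nothing in the protocol makes Table 4 the only route. This stands as a real safeguard, and it rules out the stronger reading that low output has no pathway or would go undetected. It does not close the gap: high output gets the same review and is still automated.

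A reader might also infer that the patient questions are wrong because they do not match the nurse note item by item. The documents do not support that. The questions are a screen and the note is a nurse's assessment; dysuria, dry mouth and dizziness are in the note and have no option in Questions 2 to 5 either. Whether *no gas* deserves its own tick-box is a choice between signal and noise. The ambiguity of the option remains.

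Further safeguards count: other symptom options, physiologic alerts, the coordinator's teaching on the app, discharge with home health services (section 4.2.1), and the instruction to keep reporting symptoms as the care team directs (section 4.3.1, item 5). They narrow the gap to a patient whose only sign is low volume, or gas without stool.

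It can also be said that the alerts are provisional, since finalised alerts are a study output. But the patient-to-patient tuning described under Table 4 concerns high-risk thresholds and the number of standard alerts, not the volume line. Finally, patients who are NPO or on thickeners may run low, so a flat line could add calls. That cost is real and belongs with the fix.

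**Conclusion.** The point holds as a minor patient-safety improvement. Table 4 lacks a low-output criterion although item h and the text after Table 5 require escalation below 500 cc, so a low volume with no ticked symptom and no physiologic alert starts nothing automatically. The Question 5 option is ambiguous and should be corrected at the same time.

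The omission and the ambiguity rest on the protocol's text alone. Only the 0.75 illustration uses assumptions, and it serves only to show that one change does not make the other redundant. How often such a patient would arise, and how often the nurse would miss the value, cannot be stated from the documents. A reader might infer a threat to the study's results; there is none, since no estimate, sample size or error rate depends on this.

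**What to change.** 1. Add a line to Table 4: *<500 ml ostomy output over one day*, to match item h.
2. Reword the Question 5 option so that no stool for 6 hours is ticked even when gas is passing, for example *No stool for 6 hours, even if gas is passing*. Remove or correct the bracket. The clinical team confirms the wording and decides whether a separate *no gas* option is wanted.
3. Record the date of the change. If some patients have already used the app, the 10-patient cohort will contain two versions of the item.

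**Cost.** One rule checked on at most 300 daily reports and one reworded option in at most 600 sessions. There will be some extra nurse calls, whose number cannot be sized from the documents. As an illustration only, if 1% to 5% of days (assumed) showed less than 500 ml with no other Table 4 condition, that is 0.01 × 300 = 3 to 0.05 × 300 = 15 calls to patients over the whole study. The call to the clinical RN adds nothing new, because item h already requires it.

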## physIQ Alert System – Ileostomy

Patients:

Any positive symptom (dehydration, infection, or obstruction)
≥1200 ml ostomy output over one day
A high risk alert
A predefined number of standard alerts in a day

Table 4: PhysIQ alerts system for CAPE navigator or monitoring nurse for Ileostomy

For ileostomy the thresholds for the high-risk alerts and the number of standard alerts may be changed from patient to patient based on how each case progresses and the density and frequency of alerts. Determining the optimal thresholds for these two types of alerts will be a key aim of this study. The goal is again maximizing signal while minimizing noise.

If any of these conditions listed in Table 4 are met the monitoring nurse will call the patient and go through a predefined note with the following data elements and questions.

Infection Symptom
 
 
a) Fever
 
b) Dysuria
 
c) Redness at ostomy site
 
d) Drainage or swelling at ostomy site
 
e) Other (Free Text)
 

Obstruction Symptom
 
 
a) Nausea
 
b) Vomiting
 
c) Bloating
 
d) Decreased or no ostomy output
 
e) No gas through ostomy
 

Dehydration Symptom
 
 
a) Lightheadedness
 
b) Dry mouth
 
c) Low or dark urine output
 
d) Dizziness
 
e) Increased ostomy output
 

Symptom Change (Obstruction, Dehydration, Infection) [This can show up if any symptom is picked]
 
 
1. New
 
2. Worsening
 
3. Stable
 
4. Improving
 
5. Resolved
 

Ostomy output
 
 
a) 500-1200cc
 
b) >1200cc
 
c) <500cc
 

Is patient NPO? Yes/No

Is patient on antibiotics? Yes/No

Patient is on stool thickening regimen?
 
 
a) None
 
b) Metamucil powder 1 tsp bid
 
c) Imodium 2mg bid w/ meals (20 mins before meals)
 
d) Imodium 2mg qid w/ meals (20 mins before meals)
 
e) Imodium 4mg qid w/ meals (20 mins before meals)
 
f) Stool thickening managed by clinical team
 


Alerts:
 
 
a) MCI alert
 
b) Afib with RVR alert
 
c) Tachypnea alert (First, frequent, increasing density, other alerts also present, no other concerning pulmonary comorbidities)
 

- d) Tachycardia alert (First, frequent, increasing density, other alerts also present, no other concerning Comorbidities or ostomy output uptrending or near 1200cc threshold)
- e) Other physiologic alert

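### The printed app questions do not ask about stoma-site redness, and refractory belly pain and 12-hour inability to eat or drink have no Table 5 line of their own

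*Protocol*

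**What the plan says.** All of this is in Protocol section 2.2.

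- **Stated content of the app questions (Ileostomy).** Patients are to be asked about "infectious symptoms such as fever, discharge or redness around the incision site or stoma", about dehydration symptoms, and about obstruction and other symptoms that the team finds alarming.
- **Printed questions.** The skin question, Question 3, opens "Your surgical wound is" and offers red, leaking, or opening up. Question 2 includes "You can't eat or drink anything for 12 hours". Question 4, on the belly, includes "Hurting and the pain medication don't help". The first option of Question 5, on the ostomy, is "Leaking, or your appliances do not stay on, or you are changing your pouch more than twice a day". The symptom questions are asked at 8am and 3pm.
- **Trigger (Table 4).** The symptom criterion is "Any positive symptom (dehydration, infection, or obstruction". The other criteria are ostomy output, a high risk alert, and a set number of standard alerts. The platform alerts the monitoring nurse when a Table 4 criterion is met.
- **Response (Table 5).** The nurse calls the patient and completes a note with infection, obstruction and dehydration lists. Logic lines a to y turn the entries into numbered actions. The logic is built into an EPIC note that highlights the recommended action.

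**The concern.** The cascade has three links: the app asks, Table 4 decides whether the nurse calls, and Table 5 says what happens next. They should cover the same symptoms, and in two places they do not.

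First, peristomal redness is promised as a question and has its own Table 5 lines, but it is missing from the printed options. Second, two answers that the team chose to collect twice daily have no named class at the trigger and no named action.

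What is at stake is patient contact. Where the printed logic is silent, each nurse decides whether to call, under which heading to record the answer and whom to tell. There is also a smaller analytic cost. The last paragraph of section 2.2 asks which component of the cascade best identifies patients at risk. With 10 patients, a symptom trigger that nurses apply differently makes that harder to answer.

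**Working it through.** The protocol gives no figure to reproduce. The check sets each app answer against Table 4, the note's symptom lists and logic lines a to y.

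**1. Note lists**
- Infection: fever; dysuria; redness at the ostomy site; drainage or swelling at the ostomy site; other (free text).
- Obstruction: nausea; vomiting; bloating; decreased or no output; no gas.
- Dehydration: lightheadedness; dry mouth; low or dark urine; dizziness; increased output.

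**2. Answers with a named match**
- Nausea or vomiting, swollen firm belly, and no stool or gas go to obstruction (lines i to n).
- Dark or reduced urine and more stool than usual go to dehydration (lines w to y).
- Fever goes to infection (lines s to v).

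**3. Answers without one**
- The three wound answers are clearly about infection but are not named, because lines o to r concern the ostomy site. They reach lines s to v through the free-text item.
- Refractory belly pain is in no list and in no line.
- Unable to eat or drink for 12 hours is in no list and in no line. The note's NPO field is a status used to choose between lines; it does not open one.
- For the last two, the nearest entry is again infection, other (free text). For a new symptom in a patient not on antibiotics, line s gives codes 1, 3 and 15: send the case to the clinical nurse, call that nurse, and consider a blood count.
- The leakage option is ambiguous. It can be read as an appliance problem or, loosely, as drainage at the ostomy site.

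**4. The reverse direction: Table 5 symptoms back to the app**
- Code 4 (call the ostomy nurse) appears in lines o (2, 4, 15) and q (2, 4, 15, 18) only. Lines p and r, the resolved states, carry code 2 alone. That is 2 of 25 lines.
- Both lines need new or worsening redness, drainage or swelling at the ostomy site. No printed option asks about redness there. The nearest is the leakage option, on its loose reading as drainage.

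**5. Extra calls if the gaps are closed**
- Prompts: 10 patients × 30 days × 2 per day = 600.
- Assumption, with no source in the protocol: each affected answer is the only positive one at 1% to 5% of prompts.
- Per answer: 600 × 0.01 = 6 to 600 × 0.05 = 30 calls.
- Three existing answers (pain, unable to eat or drink, leakage): 3 × 6 = 18 to 3 × 30 = 90.
- New stoma-skin option: 6 to 30.
- Total: 24 to 120 calls, or 2.4 to 12 per patient over 30 days.

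**The case against.** The strongest case is that the cascade already copes. The Table 4 wording begins with any positive symptom, and the parenthesis may only describe it, since the app's stated scope includes other alarming symptoms. The nurse reads all answers morning and afternoon and, on any call, goes through the whole note, including ostomy-site redness and drainage. Every patient is discharged with home health services (section 4.2.1), and patients are told to follow their care team's instructions on what to report at once (section 4.3.1). The smart note will be tested, and Aim 2 exists to finalize alert criteria.

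Most of this stands, and it rules out several stronger conclusions that a reader might draw:

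- **That no alert would fire for pain or inability to eat or drink.** The broad reading of Table 4 is open, so the text shows an undefined route, not a missed alert.
- **That lines o and q cannot be reached from the app.** The leakage option can be read as ostomy-site drainage, and any call can uncover stoma-site signs.
- **That leakage has no route, or that a fixed share of app options has none.** Any such count depends on how the leakage option and the free-text item are sorted. The free-text item cannot be allowed for wound answers and refused for others.
- **That the answer to "If you choose any of the above symptom(s), are the symptoms getting better, worse, or the same" has nowhere to go because the note field is headed "Symptom Change (Obstruction, Dehydration, Infection".** The bracket after that heading says the field can appear when any symptom is picked.

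The objection does not remove the mismatch. The stated content includes redness at the stoma and the printed options do not. A broad trigger settles only whether the nurse calls, not what Table 5 recommends. The free-text route files pain as infection. Testing whether the built logic is correct need not expose a missing line. Section 2.2 also describes these patients as using a standardized, already tuned alert set, and the patient-level tuning it describes concerns the physiologic alerts.

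**Conclusion.** The point holds in a limited form. One symptom promised in the text and acted on in Table 5, redness at the stoma site, is not asked by any printed option. It is a named symptom in the only 2 of 25 logic lines that call the ostomy nurse. Two answers asked twice a day, refractory belly pain and inability to eat or drink for 12 hours, have no named class and no line of their own, with infection free text as the only fallback.

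The expected consequence is inconsistent or delayed contact, softened by nurse review, home health services and patient self-report. No sample size, error rate or estimate depends on it. The conclusion assumes that the printed questions and logic are what was configured. It is a modest safety and consistency improvement that is cheap enough to make now. Leaving it to the final specifications would mean fixing it after these patients have been monitored.

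**What to change.** 1. In Table 4, state the symptom trigger as any positive answer to Questions 2 to 5.
2. Add one app option: the skin around your stoma is red, swollen or draining. This matches the stated content and feeds lines o and q.
3. Add one Table 5 line: refractory abdominal pain, or unable to eat or drink for 12 hours, to the clinical nurse with existing codes 1 and 3, for the clinical team to confirm.
4. Leave the onward routing of appliance leakage to the clinical team. A call to the ostomy nurse for each such answer trades signal against noise, and the documents do not settle that.

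**Cost.** One reworded criterion, one added option, and one added line (25 to 26), with the smart note updated to match. The running cost is extra nurse calls, at most the 2.4 to 12 per patient over 30 days worked out above under the 1% to 5% assumption. That total includes leakage answers, because the wider trigger covers them. Some of these calls may already happen where nurses read the trigger broadly. The upper end would pull against the aim of limiting noise, so the team should count calls by triggering answer from the first patient.
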